9.3 Schedule of Observations and Procedures

The schedule for all study-related procedures for all evaluations is shown in Appendix A and is not comprehensively duplicated in the following sections.

9.3.1 Observations and Procedures

9.3.1.1 Screening

Screening activities must occur within 28 days prior to randomization. Subjects will be screened in accordance with predefined inclusion and exclusion criteria as described in Section 7.0. See Section 9.1.15 for procedures for documenting screening failures. Subjects who are screening failures may be screened a second time if their reason for failing screening is thought to be resolved. Re-screened subjects will receive a new Screening number.

Subjects who have passed initial Screening procedures (Appendix A) will receive standardized instruction in how to complete the Patient Motor Diary (i.e., Hauser diary). After training, subjects and a skilled rater will complete Patient Motor Diary entries for at least 4 consecutive half-hour periods during a screening visit. The concordance testing session must include at least one ON and one OFF period; the test session will extend for up to 4 additional 30 min. periods until there is at least one in each state. Concordance must reach acceptance criterion (75%) for study eligibility.

Following a successful concordance test and prior to randomization, subjects must complete the Patient Motor Diary at home over 2 days and demonstrate (a) acceptable quality of the diary, with no more than 4 errors per day); and (b) average daily OFF time of at least 2 h and not one day below 1.0 h.

Study No. CVN424-201 Page 43 of 73

Protocol v. 4.0 14 July 2021

9.3.1.2 Study Visit, Baseline and Randomization (Day 0)

All eligible subjects who are being enrolled will present to their local site for a Baseline and Randomization visit. Baseline efficacy and safety assessments will be performed, including (but not limited to) UPDRS, CGI, PGI, Questionnaire for Impulsive-Compulsive Disorders (QUIP).

Following baseline assessments, subjects' treatment assignment will be randomized using the online interactive response system.

Arrangements will be made for the subject to attend their Day 1 visit.

9.3.1.3 Study Visit, Day 1

A urine hCG pregnancy test will be performed for female subjects of childbearing potential; pregnant women must not receive study drug.

The first dose of study drug (CVN424 or placebo) will be administered under direction of site personnel. Subjects not randomized to placebo will initiate treatment with 50 mg CVN424. Vital signs will be assessed hourly through at least 3 h post-dose. Orthostatic vital signs (non-triplicate) will be recorded pre-dose and at 3 h post-dose. Triplicate ECG will be obtained prior to dosing and approximately 3 h post-dose. Additional monitoring of vital signs and ECGs may continue beyond 3 h post-dose at the discretion of the Investigator.

Investigator or their delegate will manage incident AEs according to their medical judgment. The first dose of CVN424 may elicit an increase in body temperature and heart rate lasting several hours. These signs can be expected to spontaneously resolve within 24 h post-dose, and to lessen with repeated dosing. Antipyretic medication (e.g., Acetaminophen Extended Release Caplets, 650 mg) can be administered for symptomatic relief of fever.

A blood sample for PK analysis will be collected pre-dose and at 3 h post-dose, according to Table 5.

Subjects will be given a 10 day supply of study drug (as suspension in amber colored bottles) to be taken home and stored under refrigeration until use. Study drug will be self-administered each morning through Day 27 ± 1 day.

9.3.1.4 Study Visit, Day 8 ± 2 days

All subjects will present to their local site on Day 8 ± 2 days, returning to the site all bottles of study medication, whether empty or unused.

Subjects will not take study drug at home on the morning of the Day 8 Study Visit. Administration of the daily dose of study drug will be deferred until after collection of a blood sample for determination of the study drug "trough" concentration.

Beginning on Visit Day 8, the high-dose cohort will increase their dosage to 150 mg CVN424 per day. This step-wise increase is intended to limit the changes that the first dose of 150 mg CVN424 may elicit in vital signs (notably, increased temperature and heart rate, which were dose-dependent and not clinically significant in a healthy volunteer study). The low-dose arm will continue to receive 50 mg per day.

Study No. CVN424-201 Page 44 of 73

Protocol v. 4.0 14 July 2021

Vital signs will be assessed hourly through at least 3 h post-dose. Orthostatic vital signs (non-triplicate) will be recorded pre-dose and at 3 h post-dose. Triplicate ECG will be obtained prior to dosing and approximately 3 h post-dose. Investigator or their delegate will manage incident AEs according to their medical judgment. Additional monitoring of vital signs and ECGs may continue beyond 3 h post-dose at the discretion of the Investigator.

A blood sample for PK analysis will be collected pre-dose and at 3 h post-dose, according to Table 5. During blood sampling, one additional tube of blood plasma will be collected for archiving (frozen storage) to support potential post hoc laboratory testing (e.g., biomarkers, potential characterization of unknown CVN424 metabolites).

After safety assessments, subjects will be given a 10 day supply of study drug to be taken home and stored under refrigeration until use.

9.3.1.5 Study Visit, Day 15 ± 2 days

All subjects will present to their local site on Day 15 ± 2 days, returning to the site all bottles of study medication, whether empty or unused.

Each subject will have completed a Patient Motor Diary recording their capabilities, limitations and motor symptoms over the prior 2 days (e.g., Days 13 and 14). Site will conduct assessments to complete the UPDRS, PGI, CGI, Epworth Sleepiness Scale, and Questionnaire for Impulsive-Compulsive Disorders. An untimed sample will be collected for PK analysis.

After safety assessments, subjects will be given a 10 day supply of study drug to be taken home and stored under refrigeration until use.

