2.0 STUDY SUMMARY

Name of Sponsor(s):	Compound:	
Cerevance Beta, Inc.	CVN424	
Title of Protocol: A Phase II, Randomized, Double-Blind, Placebo-Controlled, Multicenter Study of CVN424 in Parkinson's Disease Patients with Motor Fluctuations	IND No.: 138119	EudraCT No.: Not applicable
Study Number: CVN424-201	Phase: 2	

Study Design:

This is a phase 2 study, randomized, double-blind, placebo-controlled, multicenter study of oral CVN424 at two dose levels (low-dose 50 mg, high-dose 150 mg) in Parkinson's disease (PD) patients with motor fluctuations. The overall study design is depicted and described below:

Note: Not all efficacy or safety assessments are performed at all study visits.

Approximately 135 male and female subjects with Parkinson's disease, on a stable dosage of levodopa but with an average of ≥ 2 h total OFF time/day and not less than 1 h per day, will be enrolled. Following baseline safety and efficacy assessments, subjects will be randomized to receive once-daily doses of either low-dose CVN424, high-dose CVN424, or matching placebo. The planned low-dose and high-dose levels will be 50 and 150 mg CVN424 per day, respectively. All subjects not randomized to placebo will initiate treatment with 50 mg CVN424 on Day 1; the low-dose arm will continue to receive 50 mg per day, while the high-dose arm will increase their daily dosage to 150 mg CVN424 beginning on Day 8 ± 2 days and continuing thereafter. Investigator or their delegate will manage incident AEs according to their medical judgment. Study drug will be self-administered each morning as an oral suspension. Subjects will continue their other PD medications.

Subjects will follow the study schedule presented below. Dosing on Day 1, Day 8, and Day 22 visits will be observed at the study site by Investigator or their delegate. For Visit Days 8 and 22, dosing of study drug (but not subjects' other medications) will be deferred until after collection of a blood sample for determination of the study drug "trough" concentration.

	Baseline & Random-ization	reatment ^b	Follow-up ^c
--	---------------------------	-----------------------	------------------------

Study No. CVN424-201 Page 10 of 73

Protocol v. 4.0 14 July 2021

Consent, Eligibility	Patient Motor Diary at Home	Study Visit	Study Visit	Study Visit	Study Visit	Study Visit	Study Visit	Final Study Visit
Days -28 to -1	Days -2 & -1	Day 0	Day 1 d	Day 8 ±2 days	Day 15 ±2 days	Day 22 ±2 days	Day 27 ±1 day	Day 35 ±2 days

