5.2.3 Additional and Exploratory Endpoints

Additional and Exploratory endpoints will include:

- Change from baseline in Unified Parkinson's Disease Rating Scale (UPDRS) Part I at Day 27
- Change from baseline in UPDRS Part II at Day 27
- Change from baseline in UPDRS Part III at Day 27
- Change from baseline in UPDRS Part IV question 32 at Day 27

Study No. CVN424-201 Page 21 of 73

Protocol v. 4.0 14 July 2021

• Change from baseline in UPDRS Part IV question 33 at Day 27

Change from baseline in Clinical Global Impression Scale (CGI) and Patient Global Impression (PGI) at Day 27

- Change from baseline in Epworth Sleepiness Scale at Day 27
- Change from baseline in 2-day average ON time without troublesome dyskinesia at Day 27 as recorded in the Patient Motor Diary
- Change from baseline in efficacy measures at Days 15 and 27
- Plasma PK parameters
- Possible characterization of plasma metabolites, or metabolic enzyme and transporter polymorphisms via pharmacogenomic analyses

Study No. CVN424-201 Page 22 of 73

[figure not shown]
Protocol v. 4.0 14 July 2021

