7.1 Inclusion Criteria

Subject eligibility is determined according to the following criteria prior to entry into the study:

- 1. Male or female adult who is 30 to 80 years of age inclusive at study entry.
- 2. Has idiopathic Parkinson's disease, Hoehn and Yahr stages 2-4, and is on a stable dosage of levodopa. (Stable is defined as a dosage unchanged in the 30 days prior to randomization and, in the opinion of the investigator, able to continue the current regimen throughout the month-long study without undue inconvenience or harm.)
- 3. Experiences an average of at least 2 h total OFF time/day, and at least 1 h each day, per Patient Motor Diary over 2 days during the Screening assessment.
- 4. The subject signs and dates a written informed consent form (ICF) and any required privacy authorization prior to the initiation of any study procedures.

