9.3.1.8 Final Study Visit, Day 35 ± 2 days

All subjects will present to their local site on Day 35 ± 2 days. Site will conduct assessments to complete the UPDRS, PGI, CGI, and Epworth Sleepiness Scale, as well as safety assessments. An untimed sample will be collected for PK analysis. The investigator must complete the End of Study eCRF page.

Subjects who have abnormal, clinically significant (CS) findings at the Final Study Visit may be asked, per investigator's discretion, to return to the clinic subsequently to ensure appropriate safety follow-up.

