Appendix A: Schedule of Study Procedures

Visit Number	SCREE	NING	1	2	3	4	5	6	7	Early Term- ination
Study Day:	Days -28 to -1	Days -2 & -1	Day 0	Day 1	Day 8 ±2 days	Day 15 ±2 days	Day 22 ±2 days	Day 27 ±1 day	Day 35 ±2 days	
Informed consent	X (a)									
Inclusion/exclusion criteria	X									
Demographics	X (a)									
Medical history	X(a)									
Concurrent medical conditions	X (a)									
Medication history	X (a)									
Vital signs and weight (b)	X (a)		X	X	X	X	X	X	X	X
Physical examination	X (a)		X		X			X	X	X
Height and BMI	X (a)							X	X	X
Clinical laboratory tests (c)	X (a)		X	X	X			X	X	X
Screening laboratory tests (d)	X (a)									
Patient Motor Diary (Hauser diary) (e)	X	X				X		X		
Concomitant medications	X		X	X	X	X	X	X	X	X
ECG (f)	X (a)			X	X			X	X	X
Randomization			X							
Study drug dosing (g)				< -	-	-	-	->		
DNA sample collection (h)			X							
RNA collection (i)				X						
PK blood collection (j)				X	X (k)	X	X	X	X	X
PTE assessment (1)	X		X	X						
AE assessment (m)			X	X	X	X	X	X	X	X
Study drug accountability					X	X	X	X	X	X
Unified Parkinson's Disease Rating Scale (UPDRS)			X			X		X	X	X
CGI			X			X		X	X	X
PGI			X			X		X	X	X

Study No. CVN424-201 Page 70 of 73

Protocol v. 4.0 14 July 2021

Visit Number SCREENING		1	2	3	4	5	6	7		
Study Day:	Days -28 to -1	Days -2 & -1	Day 0	Day 1	Day 8 ±2 days	Day 15 ±2 days	Day 22 ±2 days	Day 27 ±1 day	Day 35 ±2 days	Early Term- ination
Epworth Sleepiness Scale			X			X		X	X	X
Questionnaire for Impulsive-Compulsive Disorders (QUIP)			X			X		X		X
Beck Depression Inventory			X					X		X

- (a) Initial Screening items, to be completed prior to other Screening assessments. Screening activities must occur within 28 days of randomization, but may be completed in fewer than 28 days. Screening days are nominally called Day -28 to Day -1, but will not necessarily correspond numerically to the calendar days prior to the Baseline Visit. By the same convention, the Patient Motor Diary will be recorded at home over 2 consecutive days during screening, but not necessarily on the 2 days immediately prior to the Baseline visit (Day 0).

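### UPDRS Part III is rated without fixing or recording ON/OFF state or time since levodopa, which adds noise to an exploratory endpoint and blurs its meaning (minor)

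*Combined protocol and SAP*

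**What the plan says.** All references are to the protocol, version 4.0.

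- **Population.** Inclusion criterion 3 in section 7.1 reads "Experiences an average of at least 2 h total OFF time/day". The Study Summary adds "Subjects will continue their other PD medications".
- **When UPDRS is scored.** Appendix A marks Days 0, 15, 27, 35 and Early Termination. It is not scored on Days 1, 8 or 22.
- **How it is scored.** Day 0 (section 9.3.1.2): "Baseline efficacy and safety assessments will be performed, including (but not limited to) UPDRS, CGI, PGI". Day 15 (section 9.3.1.5): "Site will conduct assessments to complete the UPDRS, PGI, CGI, Epworth Sleepiness Scale". Day 27 (section 9.3.1.7) has an equivalent instruction. Day 35 (section 9.3.1.8): "Site will conduct assessments to complete the UPDRS, PGI, CGI, and Epworth Sleepiness Scale, as well as safety assessments". None of these mentions motor state, time of day or time since a levodopa dose. The UPDRS row in Appendix A carries no footnote, and footnotes (a) to (m) do not address it.
- **Endpoint.** Section 5.2.3 lists "Change from baseline in UPDRS Part III at Day 27" among the additional and exploratory endpoints. Section 12.1.5 analyses these in the same MMRM as diary OFF time, with baseline as a covariate.
- **What is standardised elsewhere.** Section 9.1.5 asks for vital signs at a consistent time of day where possible. Section 9.1 asks for the same assessor where possible. Section 9.3.1.1 requires the diary concordance session to contain both an ON and an OFF period.

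**The concern.** The Part III motor examination depends on whether the patient is ON or OFF when examined, and this trial enrols people because they move between those states every day. With no rule on state, a subject examined ON at Day 0 and OFF at Day 27, or the reverse, is fully within protocol, and that subject's change score contains the state difference as well as any drug effect.

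Two things are at stake. The first is precision: switching adds variance to the Part III change and lowers the chance of seeing an effect. The second is interpretation: a drug that shortens OFF time makes it likelier that a patient is ON at the visit. Mean Part III would then improve even if function within each state had not changed, so the result would partly restate the diary finding. This is the first study of CVN424 in patients with PD, so readers will look to Part III as supporting evidence.

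**Working it through.** **1. Is state fixed or recorded anywhere?** I set the relevant sections side by side.

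- Visit sections 9.3.1.2, 9.3.1.5, 9.3.1.7 and 9.3.1.8, and Appendix A: no state or levodopa timing for UPDRS.
- Table 5: the Day 15, 27 and 35 PK samples have no specified time, so they do not anchor the clock at those visits.
- Sections 9.3.1.4 and 9.3.1.6: deferral of the morning study-drug dose applies on Days 8 and 22, when UPDRS is not scored.
- Section 9.1.6: the concomitant medication record covers dose, frequency and start and end dates, but not the time of the last intake before a rating.
- Section 12.1.5: motor state is not a named model term. Covariates may be added before unblinding, but only if the data exist.

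State is therefore neither fixed nor captured.

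**2. The plan's own power figure.** Section 12.3 gives 80% power for a 1.5 h reduction in OFF time, with SD 3 h, 45 per arm, 20% non-evaluable and one-tailed p < 0.1.

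- Evaluable per arm: 45 × 0.8 = 36.
- SE = 3 × √(2/36) = 0.707, and 1.5/0.707 = 2.121.
- Power = Φ(2.121 − 1.282) = 0.799.

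The figure reproduces. It rests on the home diary, so Part III timing does not touch it.

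**3. Added noise, by assumption.** The documents give no UPDRS SD, effect or ON-OFF difference. Let D be the OFF-minus-ON difference in Part III and p the chance of being OFF at a rating. Assume D = 8-16 points, p = 0.15-0.35, and independent states at the two visits. For a raw change score:

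added variance = 2p(1−p)D²

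- Low end: 2 × 0.15 × 0.85 × 8² = 16.3, SD 4.0.
- High end: 2 × 0.35 × 0.65 × 16² = 116.5, SD 10.8.

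Two features make these upper figures for the assumed inputs.

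- If a subject's state is correlated across visits with correlation ρ, the variance term is multiplied by (1−ρ).
- The MMRM adjusts for baseline. With independent states, equal variances at the two visits and a fixed-state baseline-to-follow-up correlation r, the added residual variance lies between p(1−p)D² and p(1−p)D²(1+r²). The lower bound gives √(0.15 × 0.85 × 64) = 2.9 to √(0.35 × 0.65 × 256) = 7.6 points.

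**4. What that could do to power.** Assume a fixed-state SD of change of 8-10 points, a true effect of 0.5 SD, 36 per arm and one-sided 0.1. Fixed-state power is 0.80. Take D = 10 and p = 0.125-0.375, on a raw change score with independent states:

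- SD 10, p = 0.125: total SD = √(100 + 21.9) = 11.04, power 0.74.
- SD 8, p = 0.375: total SD = √(64 + 46.9) = 10.53, power 0.63.

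Over D = 5-20 the range is 0.78 to 0.42. That width shows how little can be said without a documented D.

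**5. Overlap with OFF time.** A 1.5 h reduction over an assumed 16 h waking day lowers the chance of being OFF by 1.5/16 = 0.094. The resulting shift in mean Part III is D × 1.5/16:

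- D = 8: 0.75 points.
- D = 16: 1.5 points.

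This shift needs no change in function within either state.

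**The case against.** The best case for the plan has four parts.

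- **Randomisation and blinding.** Chance motor state is balanced between arms in expectation, so with no drug effect it adds noise and not bias. This stands. A reader might infer that the Part III comparison is biased, or that the efficacy conclusions are unsafe. The documents do not support that. If the drug makes patients likelier to be ON, a better Part III at a routine visit is a real effect of treatment. No decision rule adds Part III to OFF time, so the overlap affects interpretation only.
- **Scope.** A reader might take the whole UPDRS at every visit to be affected. It is scored at four scheduled visits and Early Termination, and the argument applies to the Part III examination. The documents do not say how Parts I, II and IV are rated with respect to motor state, and nothing is shown here for them.
- **Size.** Every input specific to Part III is assumed, and both correlated states and baseline adjustment shrink the noise. This stands, and the figures are stated as upper illustrations for that reason.
- **Silence is not a defect.** Section 6.2 commits to standard scales and methods, section 12.1 promises a separate SAP and a blinded data review, and a rater manual may exist. This does not remove the point. The SAP is not in the text available to me, a rater manual is outside the documents, and neither a covariate nor a data review can use state or levodopa timing that the protocol does not ask sites to collect.

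**Conclusion.** The point holds as a minor one. Where UPDRS is scored, the protocol neither fixes nor records ON/OFF state or time since levodopa for Part III, in patients selected for fluctuating. The consequences are extra noise in the exploratory Part III change at Day 27 and a treatment difference that cannot be divided between function within a state and time spent ON.

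On the stated assumptions the noise is at most about 4-11 points of SD on a raw change score, and the overlap is 0.75-1.5 points. Neither figure has a basis in the documents beyond the 1.5 h effect. The primary endpoint (related TEAEs), the secondary diary OFF-time endpoint and the sample size are untouched.

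A reader might also infer that the remedy is to analyse only visits matched on state. That would select on a post-randomisation variable that treatment may change. The arms could then lose different subjects, which would introduce bias where there is now mainly noise.

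**What to change.** 1. In sections 9.3.1.2, 9.3.1.5, 9.3.1.7 and 9.3.1.8, and in a new Appendix A footnote to the UPDRS row, schedule Part III in one motor state named in advance. Take it at a similar time of day, and a similar interval after the subject's usual levodopa dose, as at baseline. This moves the rating only; no medication changes.
2. Record motor state and time of last levodopa dose in the eCRF at every Part III rating, including Early Termination. If the state cannot be reached, rate anyway and record the actual state.
3. In the SAP, keep all randomised subjects' Part III ratings in the main Part III analysis, with no exclusion for motor state. Use recorded state for description, or in a sensitivity analysis labelled as such.

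The cost is protocol wording, two eCRF fields and some waiting at visits. Raters and subjects already practise identifying ON and OFF for the diary concordance test. If only one step is possible, recording the two fields alone would still show how often state differed between baseline and Day 27.

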9.3.1.6 Study Visit, Day 22 ± 2 days

All subjects will present to their local site on Day 22 ± 2 days, returning to the site all bottles of study medication, whether empty or unused (time not specified).

Subjects will not take study drug at home on the morning of the Day 22 Study Visit. Administration of the daily dose of study drug will be deferred until after collection of a blood sample for determination of the study drug "trough" concentration. Following observed dosing, serial blood plasma samples will be collected for PK analysis according to the schedule in Table 5.

After safety assessments, subjects will be given a supply of study drug sufficient to last through dosing Day 27 ± 1 day to be taken home and stored under refrigeration until use.

9.3.1.7 Study Visit, Day 27 ± 1 day

All subjects will present to their local site on Day 27 ± 1 day, returning to the site all bottles of study medication, whether empty or unused.

An untimed blood sample for PK analysis will be collected.

All subjects will have completed a Patient Motor Diary recording their capabilities, limitations and motor symptoms over the prior 2 days (e.g., Days 25 and 26). Site will conduct assessments to

Study No. CVN424-201 Page 45 of 73

Protocol v. 4.0 14 July 2021

complete the UPDRS. PGI, CGI, Epworth Sleepiness Scale, and Questionnaire for Impulsive-Compulsive Disorders.

